# 1 Introduction

This document follows outlines the proposed presentation and detailed analysis for the main papers reporting results from the single-centre TirolGESUND study to investigate the impact of a lifestyle intervention on a variety of health parameters, importantly epigenetics. This and the original study protocol, available in German, follow the SPIRIT guidelines for study protocols.

The results reported in these papers will follow the strategy set out here. Any subsequent analyses of a more exploratory nature will not necessarily be bound by this strategy and will be detailed in separate analysis plans.

Suggestions for subsequent analyses by journal editors and referees will be considered carefully in line with the principles of this analysis plan. Any deviations from the statistical analysis plan will be described and justified. The analyses will be carried out by identified appropriately qualified and experienced statisticians or researchers who will ensure integrity of the data during their processing.

# 2 Background information

# 2.1 Rationale

A detailed outline of the background and rationale, including age and disease risk and epigenetic risk stratification, are detailed in the study protocol, available in German. Briefly, a majority of malignancies may be caused modifiable risk factors and could therefore be prevented. Smoking and diet are known risk factors for cancer but also other disorders such as cardiovascular or metabolic disorders and neurodegeneration, and may promote premature cellular ageing. TirolGESUND investigates the effect of two lifestyle interventions, namely smoking cessation or intermittent fasting (both with additional adjuvant exercise), over 6 months for the promotion of health and reduction of disease risk.

As investigation of disease incidence and mortality following intervention require longterm follow-up, here we explore the use of primarily epigenetic signatures indicative of disease risk as so-called "surrogate endpoints" (surrogate to follow-up of long-term followup). Our primary aim is to identify the malleability of the epigenetic cancer risk- and age-associated signature scores in this cohort of healthy-albeit-at-increased-risk women (cervical, blood, and buccal samples). Women's cancer risk identification (WID) indices have been shown to have high sensitivity and specificity in identifying current cancer patients from healthy controls, less is known about their suitability for risk prediction and continuous monitoring during lifestyle or pharmacological changes. There is preliminary evidence that WID indices may reflect systemic epigenetic field defects and enable prediction. For example, the indices are increased in women with a *BRCA1* or *BRCA2* mutation who have an increased risk for breast cancer. There are currently no prospective validation data defining thresholds for WID index positivity. Prospective validation is not the aim of TirolGESUND, instead we are assessing the impact of lifestyle intervention of such cancer risk signature scores as surrogate endpoints. As smoking and diet constistute risk factors for a variety of other diseases, including cardiovascular, neurodegenerative, pulmonary, and intestinal, we are additionally evaluating the effect of lifestyle changes on these organ systems via additional surrogate markers or clinical measures.

The study is primarily a explorative study to evaluate longitudinal impacts of lifestyle change on health markers, and may not be sufficiently powered for each measure outlined below.

# 2.2 Study objectives

#### 2.2.1 Primary objective

To assess whether a reduction and/or cessation in risk exposure (smoking, continuous nontime restricted intake of calories) via lifestyle modification over six months results in significant absolute changes in DNA methylation-based Women's cancer risk identification (WID) signature scores compared to baseline in cervical samples. WID signatures act as intermediate surrogate markers for disease risk (e.g. breast or ovarian cancer) and cellular ageing; high scores of these signatures indicate a higher risk for certain cancers, and a reduction thereof would indicate a reduced risk of later development of this disease. Successful completion relates to a significant reduction in two ore more WID risk scores with no significant in increase in any of the scores (see 5.4.1). Individuals that did not adhere to the intervention but continued to provide samples may be used as a nested control, if at least 10 individuals are present. Testing will be conducted using paired t tests or appropriate non-parametric tests. Linear or non-linear mixed-effects models may be employed.

#### 2.2.2 Secondary objectives

The TirolGESUND study is novel type of participatory, lifestyle intervention study and may represent a considerable effort for participants. Few studies have so far so comprehensively evaluated health parameters longitudinally. Therefore, we will describe and report general study characteristics relating to participation and dropout, and evaluate changes, as well as dynamics, in several biological markers, including molecular (epigenetic, genetic, microbial, metabolic), clinical, and psychological (see 5.4.2).

We are also interested in investigating the spatial and temporal dynamics of DNA methylation changes in response to lifestyle intervention and will hence be investigating changes over time in different surrogate samples (cervical, buccal, blood) using mixed-effects models, and moreover investigate whether surrogate tissue DNA methylation changes occur in a synchronous or discordant manner.

Lastly, we will explore dynamics of other biomarkers and indicators of health and disease, including microbiome, metabolome, inflammation, body composition and smoking status, vascular health, pulmonary health, physical activity, and health-related quality of life.

#### 2.2.3 Subsidiary outcomes or objectives

Subsidiary endpoints include analysis of longer-term changes at month 12 and 18 for participants who provided longer-term samples.

In a subgroup of participants (n=10), we will apply single cell multiomic analysis for RNA and ATAC-seq to investigate cellular heterogeneity at an early time point (two months

of intervention).

A subgroup of participants will be selected to investigate of which epigenetic sites are (individually) altered with cellular Yamanaka factor-induced reprogramming in samples collected at baseline (M0). In these participants we will investigated if the same or similar sites are significantly altered by the intervention at M6 (within-individual); if consistent regions are found across individuals, these sites may also applied to those individuals that were not included in reprogramming analysis.

Lastly, we may explore potential DNAme biomarkers that change in response to the intervention and are associated with clinically meaningful features (e.g. microbiome, lung function).

# 3 Study methods

#### 3.1 Study design

TirolGESUND is a single-centre, open-label baseline-controlled study that encompasses two parallel arms with 6 months of intervention. One study is aimed at investigating the effect of smoking cessation. The other study is a randomised trial that evaluates the effect of intermittent fasting with or without ketogenic supplement. The two sub-studies will be evaluated separately. The study does not include a control group but instead investigates changes compared to baseline. Individuals that do not comply with the intervention but continue to provide samples may be utilised as a nested control group. The study is predominantly of exploratory nature, although comparisons to baseline measurements will be made as outlined in the primary, secondary, and subsidiary objectives. We aim to include a total of one-hundred and eighty participants as follows:

#### 1. Smoking cessation (n = 60)

Sixty women aged 30-60 without a significant prior medical history who have been smoking above or equal 10 cigarettes a day for at least five years will be recruited and instructed to stop smoking via a professional smoking cessation programme (provided by Suchthilfe Tirol) and 1:1 personal coaching.

#### 2. Dietary intervention (n = 120)

One-hundred and twenty women without significant prior medical history with a body mass index (BMI) between 25 and 35 will be recruited and aided to conduct 16:8 intermittent fasting (16 h fasting, 8 h window for food consumption each day). The window during which food can be consumed can be freely chosen by each participant Participants will be randomly allocated one of the following groups using age- and BMI-stratified block randomisation:

• Intermittent fasting (n = 60)

Intermittent fasting has been shown to convey a series of metabolic and health benefits, promoting longevity and reducing tumour incidence in animal models. Recent human studies suggest similar benefits in humans. We aim to assess whether intermittent fasting can improve a variety of health parameters.

• Intermittent fasting with ketogenic supplement (n = 60)Intermittent fasting may mediate its benefits via timing of feeding/circadian rhythms, caloric restriction, and/or, in part, by promoting nutritional ketosis via the absence of carbohydrates; promotion of ketosis has been shown to induce longevity in mice. Ketogenic supplements are already commonly used in dietary therapy for pediatric epilepsy, but have not been routinely used in other settings. We aim to assess whether ketogenic supplements may boost ketosis and further enhance the health benefits of intermittent fasting.

# 3.2 Study setting

The study will be conducted at the EUTOPS (European Translational Oncology Prevention and Screening Institute) research clinic located at the Landeskrankenhaus Hall. Vascular examinations and optional skin biopsies are taken at the Krankenhaus Innsbruck. Sports examinations are conducted at the Institut für Sport-, Alpinmedizin und Gesundheitstourismus. Smoking cessation courses may be conducted in local seminar rooms.

# 3.3 Interventions

Participants will be allocated to the smoking cessation or dietary intervention sub-study based on inclusion criteria (described in detail in section 4.1). In the dietary intervention arm, participants will be further randomised between two subgroups. All participants will receive 1:1 personal coaching once a week in an attempt to minimise the attrition rate. Regardless of intervention group, participants will also receive an adjuvant targeted exercise program (detailed in section 3.3.4), aimed at improving overall health.

## 3.3.1 Smoking cessation

- Three smoking cessation group therapy sessions (6-12 participants per session) ideally within the first month of the study. Smoking cessation occurs in the second session. Thus, for each participant, a clearly defined (theoretical) smoking cessation date will be available
- Two individual telephone appointments with a professional addiction counsellor
- Adjuvant exercise programme and dietary guidance to promote a healthy diet at start of the study and 2 and 4 months after study initiation. These aspects were added to prevent weight gain after smoking cessation

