## 3.6 Sample size

The sample size of n = 60 per group is based on an initial estimation of the potential clinically relevant effect and variance as part of the preceding FORECEE project: a total of 60 participants are required to detect a difference of 0.2 in DNA methylation indices (e.g. WID-BC index), assuming a standard deviation of 0.44, at a statistical power of 0.94 and a significance level of 0.05. There are no preliminary data for longitudinal changes in the WID scores, thereby TirolGESUND acts as a pilot study to define effect sizes and variance for larger prospective studies in the future.

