# 6 Analysis

Analyses will be conducted and reported separately per sub-study (i.e. smoking cessation and intermittent fasting) after all samples for the month 6 timepoint have been collected. Key analyses will be performed on the ITT population. A per-protocol analysis will be conducted if sufficient individuals are available with above 80% compliance (n=30), or alternatively and additionally a subgroup analyses split by median compliance score (above and beyond, respectively). Descriptive statistics of dynamics over 6 months without an intervention will be reported and if sufficient individuals are present per study arm (n  $\geq 10$ ) that did not adhere, these may be used as a nested control group; although this number is small, it could be informative for dynamic changes without intervention.

The longitudinal manner of data collection enables baseline-controlled pairwise comparison (paired t or Wilcoxon test) for each participant at baseline and after 6 months; linear mixed effects-models may also be employed. Longitudinal dynamics and repeated measurements per participant, evaluating data from baseline, 2, 4, and 6 months, will be assessed using linear (or non-linear) mixed-effects models to account for inter-individual heterogeneity and differences in response (random intercept and slopes, if appropriate). In the intermittent fasting group, cross-sectional analyses may be used to compare effects for use with and without ketogenic supplement. Change from baseline may be reported in a descriptive manner.

Methylation data will be adjusted for sample cell type composition which is known to influence methylation levels. Many of the assessed factors are influenced by age. Dependence on other, non-intervention related covariates will be investigated during the exploratory data visualisation and assessment, and factors may be associated as covariates in mixed-effects models if necessary.

If a number of participants does not adhere to the intervention but continues to provide samples and the assumption of common support holds, we may be able to explore the average treatment effect (ATE) and causal average treatment effect (CATE) using causal inference (g methods) via covariate adjustment for selected secondary outcomes (in particular longitudinal DNA methylation analyses).

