#### 6.4.3 Primary endpoint reporting

For primary endpoint analysis, paired Wilcoxon tests will be performed on adjusted WID scores associated with disease risk, cellular ageing, or exposure, in cervical samples at baseline and month 6 of the intervention (adjusted for immune cell composition). For visualisation, points and lines may be coloured by compliance score, delta BMI, or smoking status at the end of the intervention. Data will be visualised using Spaghetti plots and may additionally be visualised using violin/box plots with overlayed jitter plots.

Analyses will be presented separately per sub-study and a comparison between the two randomised arms in the diet intervention study may be conducted. The analysis is predominantly conducted ITT, but separate subgroup analyses may be conducted as follows:

- $\bullet$  per protocol, if at least 30 individuals have a cumulative compliance score of more than 80%
- diet intervention: timing of fasting, breakfast versus dinner cancellation

Mixed-effects models could provide a complimentary method of reporting individual effects over time.

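### Smoking cessation is delivered in groups of 6-12 women, but no planned smoking-arm analysis allows for correlation within therapy groups

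*SAP*

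**What the plan says.** - **Delivery.** Section 3.3.1 (smoking sub-study, n = 60, not randomised) plans "Three smoking cessation group therapy sessions (6-12 participants per session"), ideally in the first month. Quitting takes place at the second session. The same section adds "Two individual telephone appointments with a professional addiction counsellor", and section 3.3 says "All participants will receive 1:1 personal coaching once a week in an attempt to minimise the attrition rate".
- **Primary test.** Section 6.4.3: "paired Wilcoxon tests will be performed on adjusted WID scores associated with disease risk, cellular ageing, or exposure, in cervical samples", comparing baseline with month 6.
- **Mixed models.** Section 6 gives their purpose as to "account for inter-individual heterogeneity and differences in response (random intercept and slopes, if appropriate"). The example smoking model in section 6.4.4 has a random intercept and time slope for each woman and no level above her. The covariates of these examples may change, but therapy group is not named.
- **Smoking status.** Section 6.5.3 foresees a GEE or generalised linear mixed model, again without a group level.
- **Sample size.** Section 3.6: "a total of 60 participants are required to detect a difference of 0.2 in DNA methylation indices", "assuming a standard deviation of 0.44, at a statistical power of 0.94 and a significance level of 0.05".
- **Inference.** Section 5.1 sets 5% significance and 95% confidence intervals throughout. Section 5.4.1 ties success to significant reductions in at least two scores with no significant increase in any.

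**The concern.** Women who attend the same second session share a quit date, a calendar period and the dynamics of their group. Some groups may do better than others, so women in one group may change alike. The paired Wilcoxon test assumes independent women and has no place for a group term. The random effects in the example model handle repeated measurements within a woman, not likeness between women.

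The sub-study has no control arm, so its inference rests on the standard error of the mean change from baseline. A shared group effect on change enlarges the true standard error, and an analysis that ignores it does not see this. Section 3.6 also describes the study as a pilot for effect sizes and variances. A variance that ignores groups could mislead the sizing of a later study delivered in groups. Section 6.4.1 checks laboratory clustering (beadchip, processing date), but the SAP has no counterpart for clustering by delivery.

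**Working it through.** **Inputs from the SAP.** n = 60, difference 0.2, SD 0.44, power 0.94, significance level 0.05 (section 3.6); 6 to 12 women per session (section 3.3.1).

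**Assumed.** Fixed group membership, giving 60/12 = 5 to 60/6 = 10 groups. An ICC of 0 to 0.10, where ICC is the share of the variance of the baseline-to-month-6 change that lies between groups. The SAP gives no value, and section 3.6 says there are no preliminary longitudinal data on the WID scores.

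**Step 1: the plan's own figure.** For 60 independent pairs, two-sided:

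power = Φ(0.2 × √60 / 0.44 − 1.96) = Φ(3.521 − 1.960) = 0.941

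The paired t-test gives 0.934. The required n is (0.44 × (1.960 + 1.555) / 0.2)² = 59.8, so 60. The stated 0.94 therefore reproduces with independent women and no allowance for clustering.

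**Step 2: allow for groups of m women.**

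- Design effect: DE = 1 + (m − 1) × ICC
- Width of a correct interval relative to the planned one: √DE
- Effective n: 60/DE
- Actual error rate of the test that ignores groups: 2 × (1 − Φ(1.96/√DE))
- Power with the correct standard error: Φ(3.521/√DE − 1.96)

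| ICC | m | DE | Width factor | Effective n | Error rate | Power |
|---|---|---|---|---|---|---|
| 0 | any | 1.00 | 1.00 | 60.0 | 5.0% | 0.94 |
| 0.01 | 6 | 1.05 | 1.02 | 57.1 | 5.6% | 0.93 |
| 0.01 | 12 | 1.11 | 1.05 | 54.1 | 6.3% | 0.92 |
| 0.05 | 6 | 1.25 | 1.12 | 48.0 | 8.0% | 0.88 |
| 0.05 | 12 | 1.55 | 1.24 | 38.7 | 11.5% | 0.81 |
| 0.10 | 6 | 1.50 | 1.22 | 40.0 | 11.0% | 0.82 |
| 0.10 | 12 | 2.10 | 1.45 | 28.6 | 17.6% | 0.68 |

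**Step 3: simulation check.** Group effects were simulated with zero mean change, using 40,000 runs for the paired t-test and 6,000 for the Wilcoxon test. At ICC 0.05 the error rate was 7.7% (m = 6) and 11.6% (m = 12) for the t-test, and 8.5% and 11.5% for the Wilcoxon test. At ICC 0.10 it was 11.0% and 17.7%, and 10.9% and 16.9%. The formula holds well enough for both tests.

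**Step 4: the price of adjusting.** The power column in Step 2 takes the group variance as known. A t-test on group means, with groups minus 1 degrees of freedom, has power 0.88 (10 groups) to 0.75 (5 groups) at ICC 0, and 0.80 to 0.57 at ICC 0.05.

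**The case against.** The strongest reply is that nothing in the SAP shows the ICC to be above zero. The group part is three sessions, ideally in the first month. Coaching is individual and weekly, there are two individual calls, and the endpoint visit is at weeks 25-28 (section 3.11). An ICC near 0 to 0.01 is plausible, and there the error rate is at most about 6.3%. This stands: the size is unknown and may be negligible.

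A second reply concerns the primary scores. Group therapy reaches the cervical WID scores only through quitting or related behaviour. If a score truly does not respond, differences between groups in quitting induce little correlation in it. The error rates above need group variance in the change while the mean change is zero. This also stands. It moves the weight of the point to interval coverage and to quit status, cigarettes smoked and compliance. For quit status, all women smoke at entry, so the precision of the quit rate matters and a before-after test hardly does.

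Third, the SAP does not say that groups stay together, and dropout would shrink them. At the 15-20% mentioned in section 5.4.2, groups of 6 to 12 fall to between 6 × 0.80 = 4.8 and 12 × 0.85 = 10.2 women. At ICC 0.05 that gives DE = 1 + 3.8 × 0.05 = 1.19 to 1 + 9.2 × 0.05 = 1.46. The effect is smaller but does not vanish.

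Last, the example models are open to further covariates. That permission covers the secondary models, does not name group, and leaves the primary test unchanged.

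**Conclusion.** The omission is real: no planned test, model or sample-size step for the smoking sub-study accounts for therapy group. The consequence is conditional. If changes are correlated within groups, confidence intervals are too narrow and the error rate exceeds 5%. With 6 to 12 women per group it is about 5.6-6.3% at ICC 0.01, 8-11.5% at 0.05 and 11-17.6% at 0.10; at ICC 0 there is no loss. This rests on an assumed ICC and on fixed membership.

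A reader might infer three stronger points that the SAP does not support:

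- That the intervals are known to be too narrow. This needs a positive ICC, which the SAP does not give.
- That every test in the trial is affected. No group therapy is described for the diet arm.
- That success should be denied whenever a group-adjusted interval includes zero. A variance estimated from 5 to 10 groups is unstable, adjustment costs real power (Step 4), and the SAP calls the study predominantly exploratory.

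The point therefore supports a prespecified sensitivity analysis and no change to the primary test.

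**What to change.** - **Data.** Record a therapy-group ID for each woman in the smoking sub-study, for example by the date of her second session, and note any change of group between sessions.
- **Reporting.** Report the number and size of the groups and the ICC of the month 6 change, with its uncertainty. This is useful pilot output even if it is near zero.
- **Sensitivity analysis.** Prespecify it for the smoking arm, beside the Wilcoxon test. Add group and group-by-time random effects to the mixed models, and a group level to the GEE or generalised linear mixed model for smoking status. Use a small-sample correction: for linear models Kenward-Roger, which section 6.4.4 already names, and for a GEE a corrected robust variance. Uncorrected robust errors are unreliable with 5 to 10 groups.
- **Interpretation.** Leave the success rule as it is. State in the report when a conclusion depends on ignoring therapy group.

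The cost is one extra variable, a paragraph in the SAP, and sensitivity intervals that are wider and less stable because there are few groups. A random-effects model loses less than the group-mean test in Step 4 when the group variance is near zero.
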